### 3. Endpoints

#### 3.1. Primary Efficacy Endpoint

The change from baseline in the mean convulsive seizure frequency (MCSF) in combined Titration and Maintenance Periods (T+M) in the ZX008 0.8 mg/kg/day group compared to the placebo group.

The primary endpoint will be assessed using a parametric analysis of covariance (ANCOVA). MCSF will be log-transformed prior to analysis. If the assumptions of the parametric ANCOVA model are not met, the primary endpoint will be assessed using a nonparametric ANCOVA where MCSF is rank-transformed prior to analysis.

#### 4. Key Secondary Efficacy Endpoints

The key secondary endpoints of Study 2 are:

- Change from baseline in the mean convulsive seizure frequency (MCSF) in T+M in the ZX008 0.2 mg/kg/day group compared to the placebo group.  
The change from baseline in MCSF for the ZX008 0.2 mg/kg/day group will be analyzed using the same methods as the primary analysis.
- ZX008 0.2 and 0.8 mg/kg/day dose groups compared independently versus placebo on the
  - The proportion of subjects who achieve a  $\geq 50\%$  reduction from baseline in convulsive seizure frequency.  
The proportion in each ZX008 treatment group will be compared independently to placebo using logistic regression analysis.
  - The longest convulsive seizure-free interval during T+M.  
Each ZX008 treatment groups will be compared to placebo on the longest interval using an independent Wilcoxon rank-sum test.

The additional secondary endpoints are:

- ZX008 0.2 and 0.8 mg/kg/day dose groups compared independently versus placebo on the
- The number of convulsive seizure-free days.
  - The proportion of subjects who achieve  $\geq 25\%$ ,  $\geq 75\%$ , or 100% reductions from baseline in convulsive seizure frequency.
  - The proportion of subjects with at most 1 (ie,  $\leq 1$  convulsive seizure) during T+M.
  - The change from baseline in non-convulsive seizure frequency.
  - The change from baseline in convulsive + non-convulsive seizure frequency
  - The incidence of rescue medication usage
  - The incidence of hospitalization to treat seizures
  - The incidence of status epilepticus.
  - Clinical Global Impression – Improvement rating, as assessed by the principal investigator.
  - Clinical Global Impression – Improvement rating, as assessed by the parent/caregiver.
  - The change from baseline in the Quality of Life in Childhood Epilepsy (QOLCE) score.
  - The change from baseline in the Pediatric Quality of Life Inventory™ (PedsQL) score.
  - The change from baseline in the PedsQL Family Impact module score.
  - The change from baseline in the QoL of the parent/caregiver using the EQ-5D-5L scale.

This document is confidential.

## Statistical Analysis Plan

Sponsor: Zogenix International Limited; Protocol No.: ZX008 Study 2 (ZX008-1501 and ZX008-1502)

---

- The change from baseline in the affective symptoms of the parent/caregiver using the Hospital Anxiety and Depression Scale (HADS).

### 4.1. Pharmacokinetic Endpoints

The PK endpoints of the study are:

- Steady-state plasma fenfluramine PK parameters ( $C_{max}$ ,  $AUC_{0-t}$ ,  $T_{max}$ , and  $t_{1/2}$ ) after administration of ZX008 derived using population PK methods

### 4.2. Safety Endpoints

The safety endpoints of the study are:

- AEs
- Laboratory safety (hematology, chemistry, urinalysis)
- Vital signs (blood pressure, heart rate, temperature, and respiratory rate)
- Physical examination
- Neurological examination
- 12-lead ECGs
- Doppler ECHOs
- Body weight
- BRIEF to measure cognition

### 4.3. Exploratory Endpoints

ZX008 0.2 mg/kg/day compared versus ZX008 0.8 mg/kg/day on primary, secondary, safety and PK endpoints mentioned above.

#### Exploratory Analyses due to Covid-19

Additional exploratory analyses may be conducted to determine the impact of Covid-19, including but not limited to, protocol deviations, missed visits and missing data, alternative data collection. Any exploratory analyses related to Covid-19 will be described in the Clinical Study Report.

This document is confidential.

## 5. Analysis Populations

### 5.1. Randomized / Enrolled Population

The Enrolled Population includes all subjects who signed the informed consent form. This population will be used to present overall study disposition data and the number of subjects in each study population.

The Randomized Population includes all subjects randomized to receive study treatment.

### 5.2. Safety (SAF) Population

All safety analyses will be performed on the SAF Population defined as all randomized subjects who receive at least one dose of ZX008 or placebo. Subjects will be analyzed according to the treatment group to which they were randomized.

### 5.3. Modified Intent-to-Treat (mITT) Population

The mITT Population is defined as all randomized subjects who receive at least one dose of ZX008 or placebo and for whom at least one week of diary data are available. Subjects will be analyzed according to the treatment group to which they were randomized. The primary comparison of ZX008 0.8 mg/kg/day to placebo, as well as key secondary analyses, will be performed on the mITT Population.

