### 5.4. Per Protocol (PP) Population

The PP Population includes all randomized subjects who receive at least one dose of ZX008 or placebo, complete at least 4 weeks of the Maintenance Period, and have no important protocol deviations that would have a significant impact on clinical outcome. Subjects will be analyzed according to the treatment group to which they were randomized. Protocol deviations will be reviewed and the list of deviations warranting exclusion from the PP Population will be finalized prior to study unblinding.

The primary and key secondary efficacy analyses will be repeated on the PP Population.

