#### **Missing Data Due to Dropouts:**

The issue of missing data has gained much attention subsequent to the National Academy of Science Report on the Treatment and Handling of Missing Data (NAS Report, 2010). Within the context of the studies, missing data arise from two sources: intermittent missing assessments (such as missing diary data), and as a result of dropouts prior to the end of the titration + maintenance periods.

In Study 1, only 2 (out of the 119) subjects had more than 7 days of missing diary data while on treatment (before dropout). The rates of dropout in the pivotal trials was 7.56% (9/119) in Study 1. Dropouts that are related to treatment response leave the possibility that the analysis of efficacy endpoints, which relies on assumptions of data being missing at random (MAR), may be violated. It is possible, though, that data may be missing not at random (MNAR). Differential dropouts leading to missing assessments may thus affect the inference on the primary endpoint.

The primary analysis method, in so far as it uses the convulsive seizure frequency averaged over the entire treatment period, in effect, assumes that a dropout would have followed the mean profile experienced up to that point in time when the subject dropped out from the study. Alternative, explicit, ways of addressing the issue of missing seizure data due to dropouts may be considered. (Kenward 2015) Two methods were chosen for minimal impact on variability of estimates as well as their simplicity.

It is assumed that the **planned duration** of T+M for Study 1 and Study 2 subjects is 14 weeks (98 days).

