*S1: Worst value substituted:* In this analysis, for a subject who drops out of treatment, if the convulsive seizure frequency during T+M is lower than the baseline value, the baseline value will be substituted for the subject from the point of withdrawal to the end of the planned duration of T+M. However, if it is higher than the baseline, there will be no substitution. The CSF for the planned duration of T+M will then be computed as a weighted mean of the value before dropout, and the imputed value after dropout. The weights will be the proportion of planned duration of T+M before and after dropout. The statistical analysis (parametric ANCOVA with  $\log CSF_{T+M}$  as response and  $\log CSF_B$  as covariate, along with age group, treatment (2 factors: placebo, ZX008)) will then be performed on the resulting dataset. Treatment comparisons will be based on the least squares means and standard errors obtained from the ANCOVA.

This document is confidential.

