## 8. Efficacy

The analysis of the primary and secondary efficacy parameters will be performed on the mITT population, except where noted.

The primary and key secondary efficacy analyses will be repeated on the PP Population.

All primary and key secondary variables will be analyzed for data obtained for the T+M period, and will be repeated for data obtained during the M period only.

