**Statistical Analysis Plan**

Sponsor: Zogenix International Limited; Protocol No.: ZX008 Study 2 (ZX008-1501 and ZX008-1502)

Table	14.2.15.7	Convulsive seizure frequency per 28 days During Double-blind Treatment: Parametric Analysis, by Concomitant Clobazam Use - mITT Population
Table	14.2.15.7a	Convulsive seizure frequency per 28 days During Double-blind Treatment: Parametric Analysis, by Concomitant Clobazam Use (Japan) - mITT Population
Table	14.2.15.9	Convulsive seizure frequency per 28 days During Double-blind Treatment: Parametric Analysis, by SCN1A Mutation Positive/Negative - mITT Population
Table	14.2.15.9a	Convulsive seizure frequency per 28 days During Double-blind Treatment: Parametric Analysis, by SCN1A Mutation Positive/Negative (Japan) - mITT Population
Figure	14.2.15.10	Scatterplot of Percentage Change in CSF per 28 days vs. Actual Dose Administered During Double-blind Treatment (mg/kg/day) - mITT Population
Figure	14.2.15.10a	Scatterplot of Percentage Change in CSF per 28 days vs. Actual Dose Administered During Double-blind Treatment (mg/kg/day) (Japan) - mITT Population
Figure	14.2.15.10b	Scatterplot of Percentage Change in CSF per 28 days vs. Actual Dose Administered During Double-blind Treatment (mg/kg/day) (Non-Japan) - mITT Population
Figure	14.2.15.11	Scatterplot of Percent Change in CSF per 28 days vs. Actual dose (mg/day) - mITT Population
Figure	14.2.15.11a	Scatterplot of Percent Change in CSF per 28 days vs. Actual dose (mg/day) (Japan) - mITT Population
Figure	14.2.15.11b	Scatterplot of Percent Change in CSF per 28 days vs. Actual dose (mg/day) (Non-Japan) - mITT Population
Table	14.2.15.12	Convulsive seizure frequency per 28 days – Sensitivity Analysis S1 Worst value substituted for dropouts - mITT Population
Table	14.2.15.12a	Convulsive seizure frequency per 28 days – Sensitivity Analysis S1 Worst value substituted for dropouts (Non-Japan) - mITT Population
Table	14.2.15.13	Convulsive seizure frequency per 28 days – Sensitivity Analysis S2 Differential imputation method for dropouts - mITT Population
Table	14.2.15.13a	Convulsive seizure frequency per 28 days – Sensitivity Analysis S2 Differential imputation method for dropouts (Non-Japan) - mITT Population
Table	14.2.15.14	Convulsive Seizure Frequency per 28 Days (Intermediate Missing Day and Post-Discontinuation Imputation): Parametric Analysis - mITT Population

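### Study 2's dropout sensitivity analyses run on the mITT set, so they may omit dosed subjects who stop in week one; the SAP does not say which period the qualifying diary week comes from

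*SAP*

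**What the plan says.** All references are to the Study 2 SAP.

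- **Analysis sets.** Section 5.1: "The Randomized Population includes all subjects randomized to receive study treatment". Section 5.2 uses the Safety Population (at least one dose) for safety analyses. Section 5.3 restricts mITT to "all randomized subjects who receive at least one dose of ZX008 or placebo and for whom at least one week of diary data are available". Under section 5.4, per-protocol subjects must among other things "complete at least 4 weeks of the Maintenance Period".
- **Use of the sets.** Section 8: "The analysis of the primary and secondary efficacy parameters will be performed on the mITT population, except where noted". The primary and key secondary analyses are repeated on the PP set. No efficacy analysis is assigned to the Randomized or Safety Population.
- **Reason for S1 and S2.** Section 6.4 accepts that dropout may be related to treatment response and that data may be missing not at random: "Differential dropouts leading to missing assessments may thus affect the inference on the primary endpoint". It continues: "Alternative, explicit, ways of addressing the issue of missing seizure data due to dropouts may be considered".
- **Rules.** Under S1, if a dropout's T+M frequency is below baseline, "the baseline value will be substituted for the subject from the point of withdrawal to the end of the planned duration of T+M". If it is higher, nothing is substituted. S2 fills the days after discontinuation with baseline counts in every arm.
- **Population label.** The section 15 index gives Table 14.2.15.12 as "Sensitivity Analysis S1 Worst value substituted for dropouts - mITT Population". Tables 14.2.15.13 to 14.2.15.15 carry the same mITT label.

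**The concern.** A dropout analysis asks what happens to the comparison when subjects who left are given a plausible or unfavourable outcome. If its analysis set first requires a minimum amount of post-dose diary, dropout itself can decide who is in the analysis, and the earliest leavers are never given an outcome. The requirement is a post-randomisation criterion, so it may act differently by arm.

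At stake is the reach of the robustness statement. On the mITT set, S1 and S2 speak for randomised, dosed subjects who also met the diary rule. They would not speak for all randomised and dosed subjects, although the baseline diary for the missing ones is already collected and both methods fill time after withdrawal from baseline.

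**Working it through.** **1. Where would a dosed subject who stops in week one appear?**

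| Analysis | Set | Included if the diary week must be on treatment? |
|---|---|---|
| Primary and secondary efficacy (section 8) | mITT | No |
| Primary and key secondary, repeated (section 8) | PP | No, because it needs 4 weeks of Maintenance |
| S1 (Table 14.2.15.12) | mITT | No |
| S2 and further imputation tables (14.2.15.13 to 14.2.15.15) | mITT | No |
| Safety | SAF | Yes |

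**2. What does the diary clause allow?** Section 5.3 names no period, so three readings are open.

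- *Any diary days.* The 42-day baseline diary (section 6.2) would qualify nearly every dosed subject and the exclusion would be almost empty. A dosed subject with no T+M diary days would then be in mITT with an undefined frequency, because the section 8.1 formula divides by the number of T+M days with diary data.
- *Any post-dose days.* Early leavers enter an 8-day taper (section 2.7) and are given a diary for it (section 2.8, Table 4, note h). Someone who stops on day 3 could still reach seven diary days.
- *T+M days only.* The exclusion takes effect as in the table above.

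**3. Can the rules be applied to these subjects?** S1 weights the observed and imputed frequencies by their share of 98 days. When the T+M frequency is below baseline, the weight on baseline is (98 − d)/98 for d days before dropout:

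- d = 3: 95/98 = 96.9%
- d = 6: 92/98 = 93.9%

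With no T+M diary days, S1's condition (T+M frequency lower than baseline) cannot be evaluated, so S1 needs one more line.

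**4. The plan's own figures.** Section 6.4: 9/119 = 7.56%, which reproduces. Section 2.5: 40 per arm, difference 40 points, SD 55%, two-sided 0.05. Power = Φ(40/(55 × √(2/40)) − 1.96) = 0.902, against the stated 90%, which also reproduces.

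**5. How many subjects?** The SAP gives no dropout times. At the Study 1 rate, with dropout spread evenly over 98 days (assumption), 120 × (9/119) × (7/98) = 0.648, or about 0.6 subjects across all arms. On Study 1 counts the range is 0 to 9.

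**6. What would restoring them do?** This is an illustration only. Suppose k of 40 subjects on 0.8 mg/kg/day and none on placebo were excluded, and each is restored at no change from baseline.

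- *Percentage scale, SD 55.* With placebo change 0%, the difference is 40 × (40 − k)/40. With placebo change −13% (the external figure in section 2.5), it is 53 × (40 − k)/40 − 13. Power uses the formula in step 4.

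| k | Difference (power), placebo 0% | Difference (power), placebo −13% |
|---|---|---|
| 0 | 40.0 (0.902) | 40.0 (0.902) |
| 1 | 39.0 (0.887) | 38.7 (0.882) |
| 2 | 38.0 (0.871) | 37.3 (0.859) |
| 3 | 37.0 (0.853) | 36.0 (0.834) |
| 9 | 31.0 (0.712) | 28.1 (0.627) |

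The last row puts as many dropouts as all of Study 1 in one arm and in one week. It is a bound and not a forecast.

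- *Log scale, assuming a mean log change of −0.9 in the rest of the arm.* The shift is k × 0.9/40 = 0.0225, 0.045 and 0.0675 for k = 1, 2 and 3. A ratio of 0.50 becomes 0.50 × exp(shift) = 0.511, 0.523 and 0.535.

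**The case against.** The case on the other side is strong on several points.

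- **The text does not say the diary week is post-dose.** This stands. A reader might infer that week-one leavers are certainly removed. The SAP does not support that, because baseline or taper diary days could satisfy the clause. The point is therefore conditional on the on-treatment reading. The silence is still a defect, because membership of the primary set should not depend on interpretation.
- **S1 cannot simply be applied to them.** This also stands. With no T+M diary days its condition is undefined. With very few, the rate is unstable: two seizures in two days is 28 per 28 days, and S1 leaves that in place if baseline is lower. A minimum-diary rule has a purpose, which is a reason to keep mITT as the primary set.
- **Nothing shows that these are the most informative dropouts.** A reader might infer it from the titration schedule. The SAP offers no evidence, and its Table 1 has the 0.8 mg/kg/day arm on the low-dose arm's dose for Days 1 to 4 and reaching its target only on Day 9. Losses in that arm alone are an assumption of the illustration.
- **Exclusions will be visible, and S2 is deliberately adverse to active drug.** Both are true. Section 7.1 reports SAF and mITT counts by arm, and S2 imputes against ZX008 on intermittent missing days and on the day of discontinuation. But counting excluded subjects does not analyse them, and S2 works only on those in the set.
- **The numbers are small.** Agreed. This limits the weight of the point without removing it.

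**Conclusion.** The point holds as one about coverage. S1, S2 and the related tables inherit the mITT diary requirement. If that week must be on treatment, dosed subjects who stop in the first week are in no efficacy analysis, including those meant to examine dropout.

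The size is unknown and probably small: about 0.6 of 120 subjects under even spread. With one to three such subjects, all on 0.8 mg/kg/day, the assumed 40-point difference falls to between 39.0 and 36.0 points, depending on k and the placebo change. A reader might infer that the primary result is in doubt or likely to reverse. Neither the SAP nor these figures support that.

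The point applies to Study 2 only. The Study 1 SAP (section 6.1.7) imputes nothing for efficacy and has no S1 or S2. It is a cheap improvement.

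**What to change.** - In section 5.3, state which period the week of diary data must come from. Keep mITT as the primary set.
- Run S1 and S2 (Tables 14.2.15.12 to 14.2.15.15) on all randomised subjects with at least one dose, by randomised arm, and relabel the tables.
- Add one line to S1: a subject with no T+M diary days is scored at the baseline frequency for the full 98 days. Leave S1's existing rule unchanged for subjects with some T+M diary days. S2's rule for days after discontinuation already uses baseline counts in every arm.

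This needs no new data: a population label, one sentence on the diary period, one line in S1 and probably very few extra records. The downside is a slightly less favourable sensitivity estimate, and unstable rates for subjects with only a few diary days.

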### 5.4. Per Protocol (PP) Population

The PP Population includes all randomized subjects who receive at least one dose of ZX008 or placebo, complete at least 4 weeks of the Maintenance Period, and have no important protocol deviations that would have a significant impact on clinical outcome. Subjects will be analyzed according to the treatment group to which they were randomized. Protocol deviations will be reviewed and the list of deviations warranting exclusion from the PP Population will be finalized prior to study unblinding.

The primary and key secondary efficacy analyses will be repeated on the PP Population.

### 5.5. Protocol Deviations

Major protocol deviations will be summarized overall and by site based on the SAF population. Major protocol deviations are those that have the potential to impact subject safety and/or affect data integrity and/or the efficacy conclusions. Major protocol deviations will be grouped into categories and may include categories, including but not limited to:

- Violation of inclusion/exclusion criteria
- Violation of randomization inclusion criteria
- Non-compliance regarding intake of IMP
- Inappropriate intake of concomitant medication
- Subject not discontinued as per protocol
- Other non-compliance

Multiple deviations can occur in the same subject and thus a subject can be counted in more than 1 deviation category.

Major and minor protocol deviations will be presented in a subject data listing for the enrolled population, sorted by treatment, site, and subject.

Deviations will be reviewed prior to the database lock of Study 2 data to determine which deviations will be classified as leading to exclusion from the PP population.

This document is confidential.

## 6. General Aspects for Statistical Analysis

### 6.1. General Methods

All statistical analyses will be performed using SAS statistical software (Version 9.4 or later).

Study 2 summaries will be presented by treatment group (Placebo, ZX008 0.2 mg/kg/day, ZX008 0.8 mg/kg/day).

Continuous data will be summarized using descriptive statistics including means, standard deviations, medians, lower and upper quartiles, minimum and maximum values. Categorical variables will be summarized with frequencies and percentages. Confidence intervals will be calculated for key parameters or estimates as warranted.

Two-sided statistical significance testing ( $\alpha = 0.05$ ) comparing each active treatment to placebo will be performed for the primary and secondary endpoints as described below, unless otherwise noted.

All relevant collected subject data will be included in listings. All subjects entered into the database will be included in data listings.

Unless otherwise specified in the subsequent sections, in the event of multiple assessments at a given planned time point, the latest collected value will be used for the summarization.

### 6.2. Key Definitions

**Study Day:** Study Day 1 is considered the day after Randomization Visit 3. Study day will be calculated relative to the Study Day 1. For any date on or after the Study 1, study day will be calculated as assessment date – Study Day 1 + 1. For any date prior to the Study 1, study day will be calculated as assessment date – Study Day 1. There will be no Study Day 0.

**Baseline Value:** Baseline period consists of 42 days immediately preceding Study Day 1. Any assessment performed during these 42 days preceding Study Day 1 will be considered for baseline assessment.

For the change in the frequency of convulsive seizures endpoint, baseline will include all data from the baseline period of 42 days immediately preceding Study Day 1. For all other endpoints, baseline is the last non-missing result from the Baseline period prior to Study Day 1.

